## V. Subject Enrollment

Subjects will be recruited by investigators and consented prior to participation in this study (Aims 1-3). Once consented, the participants and investigators will complete data collection in all Aims during the course of the cannula trial period.

## Sample Size:

To provide a sufficiently powered sample dataset, we will enroll up to 32 subjects to complete this study on nasal cannula designs, with a calculated sample size of N=26 plus a 20% failure/fallout rate. This will provide sufficient data to adequately inform on the study objectives.

This sample size was estimated through use of references that (1) approximated minimal clinical important difference of dyspnea (modified Borg scale) and (2) approximated expected standard deviation of prior datasets measuring dyspnea. Estimated minimal clinical important difference of dyspnea was determined to be a difference value of 2 in modified Borg for dyspnea. In reviewing publications from Roca 2010 and Schwabbauer 2014, it was estimated that a value of 2 to 3 was suitable for the standard deviation of dyspnea for the modified Borg scale. Therefore, for this study, using the paired t-test sample size calculation, with an expected difference of 2, and an expected standard deviation of 3, using a desired power of 90% with alpha=0.05, the sample size is estimated at 26 to show if the data may or may not have any difference.

#### **VI. Study Procedures**

This study is non-blinded by necessity, since the difference in cannulas can be perceived by both the clinician and patient. Patients may not know the difference between legacy and next generation cannulae, except in case of the Unicorn cannula design (as it employs a single-nasal prong). The next generation cannulae will be order-randomized after the conventional legacy cannula is used during the control evaluation. The study is a crossover design trial that will measure the ventilatory and comfort performance of nasal cannula design, specifically the effect on relief of dyspnea as demonstrated by RPD assessment, and measurement by TcPCO2 device. In addition, patient physiologic outcomes (e.g. HR, RR, BP, SpO2), and patient & clinician assessment scores will be assessed and documented. Figure 1 illustrates a flowchart of overall study procedures.

#### Screening, Enrollment, & Management

Upon screening, subjects will be asked to participate in this study, and if so, they will provide informed consent prior to enrollment. During screening, patient will be evaluated for nostril aperture areas, which will accommodate the various cannula designs without occluding greater than 50% of the aperture area of a nostril by any cannula design (per inclusion criteria #2). Subjects are instructed that if at any time during the study that they wish to discontinue the study, they are free to stop the test and discontinue study participation. All study procedures will be explained to the subject.

Upon enrollment, appropriate study data will be collected (see below under Data Collection), including patient demographics (e.g. age, gender, ethnicity, race), anthropometrics (e.g. weight, height, BMI, and applicable medical history including a detailed focus on the patient's current respiratory status (LTOT user, positive-airway pressure therapy user, current respiratory therapy). Subjects will be managed by routine care while study data is captured as shown in the timeline below (Table 1). All decision making for patient participation will be made per standard practice at the trial site, relying on the judgment of the medical staff. Using cards coded to trial patient number, the two next generation test cannulae will be order-randomized and that randomization will be determined by the clinician or study staff opening sequential numbered opaque envelopes directing such randomization. Time required from screening to the end of the study, is estimated to be two hours and fifteen minutes.

#### HVNI Cannula Efficacy in Relieving Dyspnea Confidential

Figure 1. Framework of the clinical study procedures discussed within this protocol. Each Phase is designated by a different cannula design, with 'Test' symbolizing the order-randomized new cannula designs (i.e. Unicorn and Prosoft).

## Phase 1 - Conventional Legacy cannula design (Control)

This test session is represented by Phase 1 in Figure 1, where the patient is placed on HVNI therapy with an appropriately fitted conventional legacy cannula design. Phase 1 will follow four distinct segments: (1) baseline characterization, (2) therapy acclimatization, (3) therapeutic characterization, (4) patient and clinician assessment scores. After Phase 1 is completed the next generation cannula test #1 will be able to start, as deemed appropriate by the clinician.

Baseline Characterization will be performed just prior to the therapy acclimatization segment of this Phase. If there is a reason the clinician does not deem the patient appropriate for the study, per inclusion/exclusion criteria, they may stop procedures during baseline characterization. The inpatient may be sitting or lying down in a comfortable environment. The patient will be set up and prepared for the cannula testing with appropriate data recording devices. While subject is at rest, the following data will be collected (see Table 1): RR, HR, BP, SpO2, TcPCO2 and RPD (Modified Borg scale 0-10). For the RPD, the clinician will record patient scores. The patient may or may not be on HVNI therapy at this time. The Phase 1, baseline characterization will include recording data while the patient is in an uncompromised state (e.g. ON current oxygen therapy, if applicable).

Therapy acclimatization (5 – 10 minutes) will be performed immediately after the baseline characterization segment is complete, and in accordance with site standard of care practices to maintain patient safety. The patient will be fitted with appropriately sized nasal cannula from the conventional legacy design (not to exceed 50% occlusion of the nares). Patients will be notified of best practice for the therapy, and clinicians will record whether patients prefer to keep their mouths open or closed. The acclimatization segment is the interval during which HVNI is to be titrated to provide the patient the appropriate settings for effective HVNI therapy. After the final FiO2/Flow settings are implemented and the patient is acclimatized the following data will be collected (see Table 1): RR, HR, BP, SpO2, TcPCO2 and RPD (Modified Borg scale 0-10). For the RPD, the clinician will record patient scores. Effective flow is recorded.

HVNI will be initiated per the initial settings identified below, after which settings will be titrated per standard practice for optimal effect. When patients are placed, the HVNI initial settings will be the following: FiO2 = level approximating the patient's prior prescription (e.g. if by nasal cannula [NC], 1LPM NC = 24%, 2LPM NC = 28%, 3LPM NC = 32%, etc.), Flow = 15 L/min, and Temperature = 35 - 37°C. Patients will be fit with a Vapotherm adult nasal cannula that will be applied by a respiratory therapist or other clinician skilled in management of HVNI. The flowrate can be decreased or increased as rapidly as necessary to alleviate respiratory distress and optimize patient comfort. Targets should be to provide relief of perceived dyspnea at an HVNI flow rate between 20 to 35 L/min (up to 40L/min). Starting temperature will be between 35 to 37°C; if patients find the gas temperature to be uncomfortable, it can be lowered as necessary down to 33 °C to enhance tolerance. The FiO2 will be set initially to approximate the likely previous dosage (see above) to initially to assure adequate oxygenation, but this should be adjusted to maintain a SpO2 > 88%.

Therapeutic Characterization will be performed 5-10 minutes after the therapy acclimatization segment is completed. This will provide the patient sufficient time to receive clinical effect of the HVNI therapy and

become sufficiently comfortable with the therapy and cannula. Once the respiratory therapist or other clinician skilled in management of HVNI deems that the HVNI settings are having a therapeutic effect, the following data will be collected (see Table 1): RR, HR, BP, SpO2, TcPCO2 and RPD (Modified Borg scale 0-10). For the RPD, the clinician will record patient scores.

Patient & Clinician Perception Assessments will be performed by the clinician or therapist performing this phase's testing procedures. Immediately following the completion of this phase, as soon as possible, the continuous Visual Acuity Scale (VAS) will be completed for each of the five endpoints for clinician assessment and the two endpoints for patient assessment. The patient perception/satisfaction assessments include: (1) relief of symptoms, and (2) comfort/tolerance. The clinician perception assessments include: (1) technical/clinical difficulties, (2) patient comfort & tolerance, (3) ease of use, (4) monitoring & support for therapy, and (5) expected/perceived patient outcomes.

**Upon completion of this phase**, the testing will pause for 15 minutes, until patient has returned to baseline dyspnea, prior to proceeding with the next nasal cannula design test. During this pause the patient will not perform known to worsen dyspnea. During the pause the patient will resume on their current oxygen therapy.

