## **Glossary of Definitions and Terms**

High Flow Nasal Cannula (HFNC): Nasal cannula system that delivers flow rates of respiratory gas meeting or exceeding a patient's normal spontaneous inspiratory flow demand. HFNC systems must maintain adequate heating and humidification of the delivered gas to protect the airway tissues from dryness.

High Velocity Nasal Insufflation (HVNI): a system consisting of heated and humidified gas mixtures of varying FiO2 delivered to a patient using a small-bore nasal cannula, at generally high flow rates imparted with increased velocity as compared to other standard large-bore cannulae. The flow rates of respiratory gas generally exceed a patient's normal spontaneous inspiratory flow demand. HVNI systems must maintain adequate heating and humidification of the delivered gas to protect the nasal tissues from dryness and provide patient comfort.

Non-Invasive Positive Pressure Ventilation (NIPPV): Breathing assist where a mask is strapped tightly to a patient's face and bi-level positive airway pressure is administered at an established frequency to support patient ventilation.

Intubation: The placement of an endotracheal tube to facilitate respiratory support and provide airway protection.

Respiratory Failure: The inability to maintain sufficient arterial blood oxygen saturation and/or retention of carbon dioxide levels during unassisted spontaneous breathing.

Pulmonary Rehabilitation: Exercise regimen for patients with compromised cardio-pulmonary function designed to improve pulmonary parameters.

Pulse Oximetry Reading (SpO2): Indirect measure of a patient's arterial blood oxygen saturation using pulse oximetry technology that utilizes oxygen/hemoglobin concentrations.

Resting  $SpO_2$ :  $SpO_2$  value the patient demonstrated at rest, while sitting upright and connected to the pulse oximetry monitor prior to the start of the study session. This value will be patient specific and reflect oxygen saturation.

Desaturation  $SpO_2$ : The  $SpO_2$  value considered to be the point of desaturation where the value drops below a specified threshold. This value is based on the desaturation requirement for reimbursement of oxygen therapy.

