## **II. Overall Study Objective**

The **overall objective** of this study is to evaluate the ability of HVNI next generation Prosoft nasal cannula designs to effect ventilation and related physiological responses relative to the conventional legacy cannula design, with which there are published clinical outcomes data.

The **hypothesis**: The next generation nasal cannula designs (Prosoft and Unicorn) will be comparable at relieving patient dyspnea while on HVNI, when compared to the conventional legacy cannula.

To test this hypothesis, the study will be conducted with the following specific aims:

Aim #1: Primary Outcome. The primary endpoint is the patient's targeted relief of dyspnea, as measured by the modified Borg scale (rated perceived dyspnea [RPD]) for each cannula design tested.

Aim #2: Secondary Outcomes. The secondary endpoints evaluate the patient vital signs (heart rate [HR], respiratory rate [RR], blood pressure [BP]), arterial oxygen saturation (SpO2), and arterial CO2 as measured by a transcutaneous CO2 device (TcPCO2). These measurements will be compiled for each cannula design tested.

Aim #3: Tertiary Outcomes. The tertiary endpoints evaluate both patient and clinician perception assessment scores. For patient perception/satisfaction these endpoints include: (1) relief of symptoms, and (2) comfort/tolerance. For clinician perceptions these endpoints include: (1) technical/clinical difficulties, (2) patient comfort & tolerance, (3) ease of use, (4) monitoring & support for therapy, and (5) expected/perceived patient outcomes.

These **endpoints** will establish equivalence of outcomes between the legacy cannula and the new cannula designs (both Unicorn and Prosoft) in terms of the ability to relieve dyspnea in adult hypercapnic patients experiencing dyspnea.

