## Phase 2 - Test #1 (randomized)

This test session is represented by Phase 2 in Figure 1, where the patient is placed on HVNI therapy with the order-randomized next generation cannula designs. Phase 2 will follow four distinct segments: (1) baseline characterization, (2) therapy acclimatization, (3) therapeutic characterization, (4) patient and clinician assessment scores.

Baseline Characterization will be performed just prior to the therapy acclimatization segment of this Phase. If there is a reason the clinician does not deem the patient appropriate for the study, per inclusion/exclusion criteria, they may stop procedures during baseline characterization. Sitting down in a comfortable environment, the patient will be setup and prepared for the cannula testing with appropriate data recording devices. The patient will be ON current/home oxygen therapy at this time. While subject is at rest, the following data will be collected (see Table 1): RR, HR, BP, SpO2, TcPCO2 and RPD (Modified Borg scale 0-10). For the RPD, the clinician will record patient scores.

Therapy acclimatization (5 – 10 minutes) will be performed after the baseline characterization segment is complete, and in accordance to site SOC to maintain patient safety. The patient will be fitted with appropriately sized nasal cannula (not to exceed 50% occlusion of the nares).

- IF order-randomized to the Unicorn cannula, then use the FiO2 & one-half the Flow settings from Phase 1 as a reference for the Therapeutic Settings.
  - For nostril selection of Unicorn cannula: Ask the patient to state which nostril is easiest to breathe through. Use that nostril to place the Solo/Unicorn cannula.
- IF order-randomized to the Prosoft cannula, then use the FiO2 & the Flow settings from Phase 1 as a reference for the Therapeutic Settings.

After the designated FiO2/Flow settings are implemented and the patient is acclimatized, the following data will be collected (see Table 1): RR, HR, BP, SpO2, TcPCO2 and RPD (Modified Borg scale 0-10). For the RPD, the clinician will record patient scores. Patient perception assessment will also be evaluated at this time.

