# For Phase 3, go back and repeat all procedures from Phase 2 with the difference of testing the second randomized cannula (Prosoft or Unicorn).

**Upon completion of this phase**, the study testing procedures will be deemed completed, and any final study data will be finished at this time. At this time, the patient may resume current/home oxygen therapy.

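### The posture instruction differs between the legacy phase and the two test phases, and posture is neither held constant nor recorded, so it can be confounded with the legacy-versus-new comparison

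*Combined protocol and SAP*

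**What the plan says.** The protocol's section VI (Study Procedures) gives posture separately for each phase, each time in the Baseline Characterization paragraph.

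- **Phase 1 (legacy control):** "The inpatient may be sitting or lying down in a comfortable environment".
- **Phase 2 (first test cannula):** "Sitting down in a comfortable environment, the patient will be setup and prepared for the cannula testing with appropriate data recording devices".
- **Phase 3 (second test cannula):** the site is told to "go back and repeat all procedures from Phase 2 with the difference of testing the second randomized cannula", so the Phase 2 wording applies again.

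The Glossary defines resting SpO2 as the "value the patient demonstrated at rest, while sitting upright and connected to the pulse oximetry monitor prior to the start of the study session".

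The order is fixed for the control: "The next generation cannulae will be order-randomized after the conventional legacy cannula is used during the control evaluation".

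The primary outcome in section II reads: "The primary endpoint is the patient's targeted relief of dyspnea, as measured by the modified Borg scale (rated perceived dyspnea [RPD]) for each cannula design". It does not say whether absolute on-therapy RPD or the change from each phase's own baseline is compared.

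Table 1 and the data lists in section VII contain no posture item. Section VIII plans a Wilcoxon signed rank test, or a t-test if the data look normal, with no term for posture or period.

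**The concern.** A crossover comparison relies on test conditions being the same in every phase apart from the cannula. Here the written set-up condition differs, and the split falls exactly between control and test. A patient may lie for legacy, but is described as sitting for both new cannulas. Randomizing the order of the two new cannulas cannot balance this, because legacy is never randomized.

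If posture affects RPD, respiratory rate, SpO2 or TcPCO2, then for every patient who changes position the paired difference mixes a posture effect with the cannula effect. Because position is not recorded, the effect could be neither detected nor adjusted for afterwards. The study aims to show that the new cannulas match the legacy design but plans a test for a difference, so a bias that offsets a real deficit could be read as comparability.

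This is separate from the fixed legacy-first order. Changing the order would not remove a posture rule that stays attached to the cannula, and aligning posture needs no change of order.

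**Working it through.** **1. The plan's own figure.** The Sample Size paragraph in section V uses a paired t-test with difference 2, SD 3, power 90% and alpha 0.05, and gives N = 26. With the noncentral t distribution and a two-sided test, the noncentrality is 2/3 × √26 = 3.40. Power is 90.4% at n = 26 and 89.2% at n = 25, so N = 26 reproduces. The posture issue does not alter it.

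**2. The texts side by side.**

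| | Phase 1 | Phase 2 | Phase 3 |
|---|---|---|---|
| Cannula | Legacy, always | Prosoft or Unicorn, randomized | The other one |
| Posture at set-up | Sitting or lying | Sitting | As Phase 2 |
| Position recorded | No | No | No |

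No sentence states a posture for acclimatization or therapeutic characterization in any phase, and none asks that the Phase 1 position be kept.

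**3. Possible size.** The documents give no posture figures, so these inputs are assumptions:

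- f = share of patients who lie in Phase 1, stay lying through the on-therapy reading, and then sit in Phases 2 and 3;
- d = RPD points by which lying exceeds sitting;
- absolute on-therapy RPD is compared, and titration absorbs none of d.

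Under these assumptions the bias in the mean paired difference is f × d. If a new cannula is truly worse by 2 points, the expected observed deficit is 2 − f × d. Power is for the two-sided paired t-test at n = 26. The plan considers SDs from 2 to 3, so both ends are shown.

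| f | d | Bias f × d | Share of the 2-point difference | Observed deficit | Power, SD 3 | Power, SD 2 |
|---|---|---|---|---|---|---|
| 0 | any | 0 | 0% | 2.00 | 90.4% | 99.8% |
| 0.25 | 1 | 0.25 | 12.5% | 1.75 | 81.6% | 99.0% |
| 0.5 | 1 | 0.50 | 25% | 1.50 | 68.8% | 95.7% |
| 0.5 | 2 | 1.00 | 50% | 1.00 | 37.3% | 68.8% |

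The SD is held at the stated value. A mix of lying and sitting patients adds f(1 − f)d² to the variance. At f = 0.5 and d = 1 that is 0.25, so the SD becomes √(9 + 0.25) = 3.04 and power is 67.6% rather than 68.8%, a minor change.

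**4. With no true difference.** With that extra variance included, the chance of a significant result rises from 5% to 13% (SD 3) or 22% (SD 2) at f = 0.5, d = 1.

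**5. If change from phase baseline is compared.** A posture held throughout a phase enters both the baseline and the on-therapy reading, so it largely subtracts out. A patient who starts Phases 2 and 3 at a lower RPD because of sitting also has less room to improve, which would count against the new cannulas. The formula f × d does not apply to this comparison.

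**The case against.** A reader might infer that patients will lie for legacy and must sit for the new cannulas, and that the new cannulas will therefore look better. The documents do not support that reading, for four reasons.

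- **Lying is permitted, not required.** A site that seats everyone in every phase complies fully, and the bias is then zero.
- **Both posture sentences concern baseline set-up.** That the position persists to the on-therapy reading is an inference. It is a reasonable one: Phase 2 describes set-up for the cannula testing, acclimatization in Phase 1 follows immediately, and no later step changes position. It is still not a stated rule.
- **The direction is not established.** The documents do not say that sitting eases dyspnea, and section II leaves open whether absolute RPD or change from baseline is used.
- **The effect may not pass through in full.** In Phase 1, flow is titrated toward relief of dyspnea. In Phases 2 and 3, flow is raised if relief is not comparable. Each new phase waits for return to baseline dyspnea. Part of d could be absorbed before the reading.

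It can also be said that the Glossary's sitting-upright wording describes a value taken before the session, under a term that the procedures and endpoints do not use. That is fair: it is an inconsistency to tidy, not a third operative rule.

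These points limit the size and remove any claim about direction. They do not remove the difference in wording between control and test, the absence of a posture record, or the inability of the randomization to balance posture against legacy.

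**Conclusion.** The concern holds as a possible confounder of unknown frequency, size and direction. The bias in an absolute-RPD comparison ranges from zero, if no one lies down in Phase 1, up to f × d. The middle case shown, 0.5 points, is a quarter of the plan's important difference. The 1-point case needs half the patients lying and a posture effect as large as that whole difference, so it should not be taken as expected.

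The figures rest on assumed f and d, on posture carrying through to the on-therapy reading, on no absorption by titration, and on absolute RPD being compared. A bias in favour of the new cannulas needs, in addition, that sitting eases dyspnea.

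Severity is moderate: the plan is workable without the change, but the gap is cheap to close beforehand, and position that was not recorded cannot be recovered later.

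**What to change.** 1. Reconcile the Phase 1 and Phase 2 baseline sentences into one posture instruction that covers all three phases and all segments, with each patient kept in the same position across phases where feasible. Align the Glossary definition of resting SpO2 with it for consistency.
2. Add position to the data lists in section VII and record it on the CRF at each RPD and TcPCO2 reading.
3. Add to section VIII a sensitivity analysis limited to patients with the same posture in all phases.

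Cost: a few sentences and a short CRF entry at each of the nine scheduled readings per patient (three segments × three phases), plus one more whenever acclimatization is repeated. No extra patients or visits are needed. A change of position need only be recorded; it need not count as a deviation, since inpatients may well shift during a session estimated at two hours and fifteen minutes. The sensitivity analysis will be smaller than the main one and should be presented as supportive.
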